**PARTNERS HUMAN RESEARCH COMMITTEE
DETAILED PROTOCOL**

MGH Vasculitis and Glomerulonephritis Program

Maintenance of ANCA vasculitis remission by intermittent rituximab dosing based on B cell reconstitution vs a serologic ANCA flare. (MAINTANCAVAS)

I. Background and Significance

Anti-neutrophil cytoplasmic antibody (ANCA) vasculitis is a systemic autoimmune disease characterized by small vessel inflammation caused by pathogenic autoantibodies directed against proteinase 3 (PR3) or myeloperoxidase (MPO)(1). The disease is highly morbid, with greater than 80% of patients suffering serious complications from irreversible organ damage or treatment-related adverse events.(2)

The devastating complications of ANCA vasculitis warrant prompt and aggressive immunosuppression. Treatment is divided into two phases: induction immunosuppression to achieve remission, and maintenance immunosuppression to prevent relapse. Cyclophosphamide has traditionally been used as the backbone of induction regimens for ANCA Vasculitis. While effective, cyclophosphamide is associated with serious adverse events including infection, gonadal toxicity leading to infertility, bone marrow suppression, and malignancy(2-4). These complications have spurred the search for novel treatments with more favorable toxicity profiles. Recently, the anti-CD 20 monoclonal antibody rituximab has emerged as an acceptable alternative to cyclophosphamide for induction therapy of AV(5,6).

Azathioprine has traditionally been the preferred agent for maintenance therapy(7). However, this strategy remains inadequate, with approximately 33% of patients relapsing at 2.5 years and a significant burden of treatment-related adverse events(8). Similarly, rituximab induction without subsequent maintenance therapy leads to unacceptable relapse rates(9). To circumvent these shortcomings, strategies employing continuous B cell depletion with maintenance rituximab dosing have been attempted. In the largest study to date, we demonstrated that rituximab administered to maintain continuous B-cell depletion produces outstanding results with a 2 year major relapse rate of 5% and a survival that mirrors the general population(10). Furthermore, a recent randomized trial confirmed that maintenance therapy with rituximab administered every 6 months is superior to daily azathioprine(11).

Despite yielding promising outcomes, rituximab is also associated with a number of adverse events including infectious complications and late onset of neutropenia(9,12). Furthermore, the complications of continuous B cell depletion for extended durations are unknown. One of the major goals in the field is to utilize prolonged B cell depletion only in the subpopulation of patients where the risk of disease relapse outweighs the risk of treatment-related adverse events.

A rise in ANCA titers and reconstitution of B cells are promising biomarkers of impending disease relapse following treatment with rituximab(9,13,14). We therefore propose a randomized trial in which these two biomarkers are used to guide additional treatment in patients who have completed at least 2 years of successful rituximab maintenance therapy.

The ANCA Assay

Our group was the first to demonstrate the association of ANCA with the neutrophil serine protease, proteinase 3 (PR3)(15). Since this time, our group has conducted numerous studies regarding the use of the ANCA assay in the diagnosis and management of ANCA vasculitis. In one investigation, 100% of patients in clinical remission who sustained a fourfold rise in ANCA titer without receiving immunosuppression relapsed at mean time of 5.8 months(13).

Rituximab for Maintenance Therapy in ANCA Vasculitis

Our group was one of the first to use rituximab as maintenance therapy for ANCA vasculitis in April of 2006. We subsequently reported that continuous B cell depletion using rituximab was highly successful for early maintenance of remission in 39 patients with ANCA vasculitis(16). This maintenance strategy was the first to use a regimen of scheduled rituximab administration in order to prevent B cell re-population.

[figure not shown]
We recently reviewed the long-term results of 172 ANCA vasculitis patients cared for by our group who underwent rituximab-induced continuous B cell depletion for maintenance of remission and found that remission was maintained in the majority of patients with a very low rate of major relapse. Most importantly, we found that this remission maintenance strategy appears to result in long-term survival matching that of the general U.S. population(10) (see Figure).

Relapse after Discontinuation of Rituximab

Data from randomized clinical trials and observational studies suggest relapse is common if rituximab is discontinued indefinitely. Among patients in the RAVE trial who achieved complete remission following treatment with rituximab, 32% had a relapse within 18 months(9).

Furthermore, Alberici *et al* reported that 41% of patients who received maintenance rituximab every 6 months for 24 months relapsed at a median of 34.4 months following discontinuation of therapy(17). Predictors of relapse included return of B cells and change from ANCA negativity to positivity(17).

Survival of ANCA vasculitis patients undergoing rituximab-induced continuous B cell depletion

A prospective and longitudinal clinical trial is needed to determine the ideal treatment strategy for long-term maintenance of remission. Here we propose to compare 2 strategies once patients have

been in sustained remission on scheduled rituximab dosing with a goal of undetectable B cells for greater than or equal to 2 years. Target enrollment is 200 subjects over 48 months from the time the first patient is enrolled to be followed for a common close out date of 36 months after the last subject is enrolled.

The study design is an open-label, single center, randomized and two-arm controlled trial to evaluate the optimal maintenance of remission strategy that provides the best relapse-free survival in patients with ANCA vasculitis as determined by relapse-free remission at 18, 24 and 36 months from enrollment. Subjects with ANCA vasculitis in sustained remission on regularly scheduled rituximab infusions with a goal of undetectable B cells for a minimum of two years who meet specific entry criteria will be randomized with stratification based on ANCA subtype and rituximab vintage (i.e., duration of continuous rituximab prior to enrollment) to one of two arms :

- 1. Intermittent B cell depletion with rituximab re-dosing upon B cell return:** Subjects will no longer receive regularly-scheduled every six-month doses of rituximab and will instead be seen in clinic with B cell monitoring every 3 months (beginning 6 months after their last rituximab dose). B cell levels will be determined by the number of CD20 positive cells detected by peripheral blood flow cytometry. Subjects will not receive rituximab if the B cell level remains < 10 cells/mm³. Once peripheral B cells levels rise to ≥ 10 cells/mm³, they will receive rituximab 1000 mg IV x 1 dose. If patients receive rituximab they will become B cell depleted, but will stay on their original study schedule. Following B cell depletion, subjects will be seen in clinic every three months, and B cell monitoring every 3 months will continue as scheduled. Patients will continue to be dosed with rituximab each time the B cell count rises to 10 cells/mm³. In the unique scenario that the B cells are detectable, but less than the threshold of 10 cells/mm³, subjects will be asked to return in 6 weeks for repeat B cell testing.
- 2. Hold continuous dosing with rituximab with re-dosing upon significant ANCA titer increase:** Subjects will no longer receive regularly scheduled every six-month doses of rituximab, and will instead be seen in clinic with the ANCA titer monitoring every three months (beginning 6 months after their last rituximab dose). For MPO, a significant increase will be defined as a 5-fold rise in ANCA titer and a level greater than 4 times the cutoff value for the assay. For PR3, a significant rise will be defined as a 4-fold rise in ANCA titer to a level at least twofold above the cutoff value for the assay. Patients who sustain a significant increase in ANCA titer will receive rituximab 1000mg IV x 2 doses (~2-3 weeks apart). If the ANCA titer then falls to less than twofold above baseline or falls below the specified threshold (the cutoff value of the assay for PR3 and 4 times the cutoff value for MPO) after rituximab, patients will be seen in clinic every three months, with monitoring of ANCA titers. However, if the ANCA titer remains twofold above baseline and above the specified threshold (the cutoff value of the assay for PR3 and 4 times the cutoff value for MPO) after rituximab, patients will continue to receive rituximab 1000mg IV every 6 months for a maximum of 2 doses, at which time a new baseline ANCA titer will be established. Once the new baseline ANCA titer is established, the patients will continue to be seen in clinic every 3 months, with monitoring of ANCA titers. Patients will continue to be dosed with rituximab each time they meet criteria for a significant ANCA titer rise. In this arm, rituximab administration is not contingent upon B cell levels. Rituximab will only be dosed based on the ANCA titer as described above. Baseline ANCA titer will be recalculated to an average of the two highest of the last four values if all four are less than the original baseline. Patients in

the ANCA arm will move to once yearly CD20 testing after CD20 levels return to normal levels (>90 cells/uL).

Patients can be treated at any time during the study period with a total prednisone dose of ≤ 7.5 mg. Patients with a disease flare (defined by BVAS/WG ≥ 2) will have reached the primary endpoint and will be treated for relapse at the discretion of the investigator

II. Specific Aims

- 1. Primary Aim: To determine whether a rituximab-dosing protocol based on: 1) reconstitution of peripheral B cells or 2) a serologic ANCA flare is more efficacious in preventing relapse in patients with ANCA vasculitis.** Eligible patients will have completed a minimum of 2 years of rituximab maintenance therapy without relapse. The endpoint will be disease relapse defined as a BVAS/WG ≥ 2 . Analysis will also be stratified based on ANCA subtype (due to differences in relapse between patients with MPO and PR3 ANCA) and rituximab vintage.
- 2. Secondary Aim 1: To determine whether a rituximab-dosing protocol based on: 1) reconstitution of peripheral B cells or 2) a serologic ANCA flare is associated with more serious adverse events.** Serious adverse events of interest include those related to vasculitis activity and those that develop as a consequence of rituximab therapy. The main rituximab-associated serious adverse events noted in our cohort are infection, late-onset of neutropenia, and infusion reactions(10)
- 3. Secondary Aim 2: To determine whether a rituximab-dosing protocol based on: 1) reconstitution or peripheral B cells or 2) a serologic ANCA flare is associated with a greater composite of disease relapse (BVAS/WG ≥ 2) and serious adverse events.**
- 4. Secondary Aim 3: To determine whether a rituximab-dosing protocol based on: 1) reconstitution of peripheral B cells or 2) a serologic ANCA flare is associated with greater rituximab utilization during the study period.** While effective, rituximab therapy is costly and increases health care expenditures. Evaluation of the relative cost of the 2 dosing-strategies will assist in the application of these dosing-strategies to the broad population of patients with ANCA vasculitis.

III. Subject Selection

Patients with ANCA vasculitis who are seen at MGH will be recruited as subjects and inclusion and exclusion criteria are detailed below.

A. Inclusion and exclusion criteria

Inclusion criteria:

1. All patients must be able and willing to give written informed consent and comply with the requirements of the study protocol.

2. Diagnosis: ANCA vasculitis as defined by a positive MPO- and/or PR3-ANCA test together with clinical features characteristic of ANCA-positive diseases as detailed in the 2012 Chapel Hill Consensus Conference Definitions(18).
3. eGFR \geq 20 cc/min/1.73m²
4. Age: 18-82 years old
5. Treated with continuous rituximab at regularly scheduled intervals with a goal of undetectable B cells for at least 24 months.
6. In sustained remission (defined by a modified BVAS-WG=0 **AND** a prednisone dose of \leq 7.5mg for at least 12 months).
7. Undetectable (<10mm³) B cells as quantified by the number of CD20+ cells on peripheral blood flow cytometry on day 0.
8. Urine Hcg negative for women of child bearing potential and not planning to become pregnant for at least 12 months from enrollment and at least 12 months after any study related rituximab dose
9. Judged to be otherwise healthy by the Investigator, based on medical history and physical examination (no known active disease process for which life expectancy is less than 36 months)

Exclusion criteria:

1. Secondary Disease: disease suspected to be induced by levamisole-adulterated cocaine
2. All transplanted patients
3. Treatment: additional immunosuppressive agents other than rituximab and/or total daily prednisone dose \geq 7.5 milligrams
4. Hypogammaglobulinemia: IgG level < 300mg/dL
5. Terminal cancer or other primary illness with life expectancy of less than 36 months
6. Active anti-GBM disease and other known autoimmune disease for which the need for additional immunosuppression is likely
7. Pregnancy or breastfeeding

B. Sources of subjects and recruitment methods

Subjects will be recruited from the current pool of patients in the MGH Renal and Rheumatology Units of the Vasculitis and Glomerulonephritis Center.

IV. Subject Enrollment

A. Methods of enrollment

Patients will be prescreened for eligibility by research staff prior to their scheduled rituximab infusion. Potential subjects will be assessed for eligibility utilizing existing data regarding current length of treatment with rituximab, prednisone dose (if any) and most recent Birmingham Vasculitis Activity Score.

At a regularly scheduled clinic visit, study site personnel will assess a patient's eligibility for enrollment, including review of the inclusion and exclusion criteria. Patients meeting all the inclusion criteria and have no exclusionary criteria and receive treatment for their ANCA Associated Vasculitis by physicians in the MGH Renal and Rheumatology Unit's Vasculitis and Glomerulonephritis Center will be offered the opportunity to participate in this study as part of their ongoing treatment.

B. Procedures for obtaining informed consent

When a potential subject is identified, the research nurse will initially explain the study to the patient after their clinical visit with [name], [name], or [name]. If the patient expresses further interest in participating in the study, [name], [name], or [name] and the research nurse will then review the study details with the patient. The patient will be provided the opportunity to take the consent form home to further review and will follow-up with the research nurse or investigator within 14 days. If they decline participation, they will continue to receive their standard of care as deemed appropriate by their treating clinician. Massachusetts General Hospital is expecting to enroll up to 200 subjects over 36 months.

C. Treatment assignment and randomization

Each subject will be stratified prior to randomization to ensure MPO- and PR3-ANCA serotypes and duration of rituximab therapy are approximately equal within each arm. Randomization will occur using random permuted blocks to assign each subject to one of two arms:

1. Treatment upon B cell return, OR
2. Treatment upon a significant rise in ANCA titer as defined above.

V. Study Procedures

A. Study visits and parameters to be measured

1. Potential subjects will be identified during a clinical visit. Medical records will be reviewed by study staff and if found eligible then the potential subjects will be offered the opportunity to participate in the study at that visit. Potential subjects will have 14 days to decide on participation.
2. "Day 0" is defined as the date of the last rituximab infusion prior to randomization and must be 6 months +/- 14 days from Study visit 1. Existing data will be collected from this date once enrolled and randomized.
3. **Study Visit 1: Enrollment and Randomization**
 - a. Patients who agree to participate and have signed and dated the consent form will be randomly assigned to one of two treatment arms:
 - i. **Arm 1:** Subjects will not receive their regularly-scheduled dose of rituximab, but will be asked to return to clinic for a follow-up visit 6 months after their last rituximab infusion. Subjects will then receive blood work and scheduled clinic visits every three months thereafter. Once B cell return occurs, as defined as ≥ 10 cells/mm³, subjects will be scheduled to receive rituximab 1000 mg IV x 1 dose. If a dose of rituximab is administered, the patient study schedule will not be adjusted. Patients will continue to be evaluated every three months per study protocol. If the B cells are detectable but <10 cells/m³, subjects will not be redosed, but will be asked to return in 6 weeks for repeat B cell monitoring.

Arm 2: Subjects will not receive their regularly scheduled dose of rituximab, but will be asked to return to clinic for a follow-up visit 6 months after the last rituximab infusion. Subjects will then receive blood work and scheduled clinic

visits every three months thereafter. If the ANCA titer has increased above the threshold for treatment described above, then the patient will be re-dosed with rituximab 1000mg IV x 2 doses 2-3 weeks apart. If the ANCA titer remains twofold above baseline and above a specified threshold (the cutoff value of the assay for PR3 and 4 times the cutoff value for MPO), patients will continue to receive rituximab 1000mg IV every 6 months for a maximum of 2 additional doses, at which time a new baseline ANCA titer will be established. Subjects will continue to be evaluated every three months per protocol schedule.

- b. A detailed history and physical examination will be performed along with the following disease assessment surveys and blood and urine measurements:
 - i. Demographic characteristics
 - ii. Date of initial physician's diagnosis of ANCA vasculitis
 - iii. Length of continuous B cell depletion treatment
 - iv. Medical history
 - v. Vasculitis Damage Index (VDI) Score
 - vi. Modified Birmingham Vasculitis Activity-WG (BVAS-WG) Score
 - vii. Any adverse events since last infusion of rituximab
 - viii. Prior and concomitant medications
 - ix. Height and weight
 - x. Blood work including but not limited to:
 1. Complete Blood Count
 2. Comprehensive Metabolic Panel
 3. eGFR
 4. ANCA titer

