Rituximab (Rituxan, Genentech), which is FDA-approved for GPA and MPA, will be used in the study.

C. Devices to be used

Not applicable

D. Procedures/surgical interventions

Not applicable

E. Data to be collected and when the data is to be collected

At present, there is no standard of care for maintenance of remission in ANCA vasculitis beyond the two-year mark; thus, the role of continuous versus intermittent B cell depletion requires investigation. Efficacy and toxicity are the foci of our outcome analysis for this study and will be assessed through analysis of primary and secondary endpoints.

The following variables will be collected at EACH study visit:

1. VDI (every 6 months)
2. Modified BVAS/WG
3. Laboratory data at baseline and at subsequent visits
 - a. Complete Blood Count
 - b. Comprehensive Metabolic Panel
 - c. eGFR
 - d. ANCA titer
 - e. ESR
 - f. CRP

- g. Immunoglobulin levels (every 6 months)
 - h. Urinalysis
 - i. Urine Hcg for women of child bearing potential (only at screening and when reinfused with rituximab)
 - j. Flow cytometric analysis of peripheral B and T lymphocyte markers
4. Concomitant medications at each visit
 5. Adverse events assessment

VI. Biostatistical Analysis

A. Specific data variables being collected for the study (e.g. data collection sheets)

Data variables collected are listed above and we will also verify contact information at each visit to ensure appropriate follow-up.

B. Study endpoints

Primary endpoints:

1. Disease flare defined as a BVAS/WG ≥ 2 . A subgroup analysis will be performed by ANCA subtype.

Secondary endpoints:

1. Proportion of patients with serious adverse events (SAEs), including all episodes of Late Onset Neutropenia (LON, absolute neutrophil count < 1000 cells/mm³)
2. The composite of disease flare (defined as BVAS/WG ≥ 2) and serious adverse events.
3. Total rituximab utilization during the study period
4. Accrued organ damage as assessed by the Vasculitis Damage Index (VDI)
5. Patient quality of life assessment using the SF-36v2 and EQ-5D-5L surveys every 6 months
6. Number of major (modified BVAS-WG ≥ 3) relapses
7. Survival
8. Hypogammaglobulinemia (IgG < 400 mg/dL)
9. All infections

C. Statistical methods

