Data will be analyzed by the intention-to-treat principle. Randomization will be stratified on ANCA subtype (MPO vs PR3) and rituximab vintage (< 3 years vs > 3 years). Rituximab vintage is the duration of continuous rituximab therapy administered prior to enrollment in the study. We have contracted with the company StudyTRAX to perform randomization on stratified variables via random permuted blocks.

Continuous data will be summarized using descriptive statistics. Continuous data will be assessed using the t-test or Wilcoxon rank-sum test as appropriate. Categorical data will be assessed using the Chi-square and the Fisher exact tests as appropriate. The probability of remaining free of relapse will be estimated using the Kaplan-Meier method. The difference between the two

treatment strategies will be assessed using the log-rank test. *P* values of 0.05 will be considered significant.

D. Power analysis

Using a two-sided logrank test with an alpha level of 0.05, a projected relapse risk of 15% in the superior group and 30% in the inferior group, and an estimated enrollment time of 36 months, it was determined that 180 patients are required to detect a significant difference with a power of 0.80. We aim to enroll 200 patients in the study.

VII. Risks and Discomforts

Subjects may experience side effects while receiving rituximab, which is given as part of their regular medical care for their GPA or MPA. As per the entry criteria, subjects have been on rituximab for 2 years prior to enrollment, the side effects have been discussed in detail and a signed consent for rituximab is obtained for every patient receiving rituximab at the first dose and annually thereafter.

The effects of rituximab on a fetus are unknown and may be harmful. Individuals of childbearing potential should use effective birth control during treatment and for 12 months after their last rituximab infusion. Prior to any infusion of rituximab to a woman of childbearing potential, a urine pregnancy test is performed and recorded. If a woman is found to be pregnant, she will then be removed from the study and followed based on best medical judgment as deemed appropriate by the clinician investigator.

A. Complications of surgical and non-surgical procedures

Not applicable

B. Drug side effects and toxicities

Common side effects of Rituxan

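### Do the 18-, 24- and 36-month time points leave open which comparison decides the primary question?

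*Combined protocol and SAP*

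**What the plan says.** Four places bear on the point, all in the combined protocol and SAP.

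- **Section I, study-design paragraph.** The trial looks for the strategy "that provides the best relapse-free survival in patients with ANCA vasculitis as determined by relapse-free remission at 18, 24 and 36 months from enrollment". Follow-up runs to a common close-out 36 months after the last enrolment.
- **Section II, Primary Aim, and section VI.B.** "The endpoint will be disease relapse defined as a BVAS/WG ≥ 2" in the first; "Disease flare defined as a BVAS/WG ≥ 2" in the second. Neither gives a time point or a test.
- **Section VI.C.** The chance of staying free of relapse is to be estimated by Kaplan-Meier, and the very next sentence says that the difference between the two "treatment strategies will be assessed using the log-rank test". The same section has two general rules: "Categorical data will be assessed using the Chi-square and the Fisher exact tests as appropriate", and p "values of 0.05 will be considered significant".
- **Section VI.D.** The sample size is found "Using a two-sided logrank test with an alpha level of 0.05", with relapse risks of 15% and 30%, 36 months of enrolment and 80% power. The result is 180 patients, with a target of 200.

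**The concern.** The phrase in section I is worded as a decision: the better strategy is determined by status at three fixed times. Section VI.C uses one test over all follow-up, which with 36-month accrual is 36 to 72 months per patient. Relapse status at a fixed month is categorical. A literal reader could therefore apply the general chi-square or Fisher rule at each time and call any p value of 0.05 significant. That would give four comparisons with no ranking and no multiplicity rule.

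Two things would be at stake. The chance of some false-positive result on the primary outcome would exceed 5%. Two analysts starting from different sections could also report different verdicts on the same data.

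The outcome might seem to shift too. The only definition of remission is inclusion criterion 6 in section III.A, "In sustained remission (defined by a modified BVAS-WG=0" together with a prednisone limit, whereas the endpoint is a score of 2 or more. A score of 1 is neither.

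**Working it through.** **1. Does 180 belong to the log-rank test?**

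Inputs from VI.D: risks 15% and 30%, two-sided alpha 0.05, power 0.80, accrual 36 months. From section I: 36 months minimum follow-up. Assumed, because the plan does not say: 1:1 allocation, risks that apply at 36 months, exponential times, uniform accrual, no loss.

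- Hazard ratio = ln(0.85)/ln(0.70) = 0.1625/0.3567 = 0.456.
- Freedman events = (1.960 + 0.842)² × [(1 + 0.456)/(1 − 0.456)]² = 7.85 × 7.15 = 56.1, so 57.
- Event probability with follow-up uniform on 36 to 72 months: 1 − (0.85 − 0.7225)/0.1625 = 0.215 and 1 − (0.70 − 0.49)/0.3567 = 0.411; mean 0.313.
- N = 57/0.313 = 182, against 180 stated.

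The match is not unique. Schoenfeld's formula gives 51 events and 163 patients on the same inputs. Freedman's with 24-month risks and 18 months minimum follow-up gives 183. A comparison of 15% with 30% at a fixed time needs 121 per arm, or 242. The stated figure therefore fits a log-rank design and does not fit a fixed-time design.

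**2. What would testing all four do?**

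Simulation: 200 patients, the assumptions above, Pearson chi-square at each time point, every test at two-sided 0.05.

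| No true difference (22.5% in both arms) | Rejects |
|---|---|
| Log-rank alone | about 5% |
| Any of the three time points | 10.1% (Fisher 6.5%) |
| Any of the four | 12.2% (Fisher 9.0%) |

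Other common risks, 180 instead of 200 patients, or 48-month accrual move the any-of-four chi-square figure only between 11.6% and 12.8%.

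| True risks 15% and 30% at 36 months | Power at 200 | Expected events used |
|---|---|---|
| 18 months | 46% | 100 × (0.078 + 0.163) = 24 |
| 24 months | 57% | 100 × (0.103 + 0.212) = 31 |
| 36 months | 73% | 100 × (0.15 + 0.30) = 45 |
| Log-rank to close-out | 86% | 200 × 0.313 = 63 |

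All four agree in 51% of trials. In 15% the log-rank test is significant and the 36-month comparison is not; in 11% it is significant and none of the three time points is. In 3% the log-rank test is not significant but some time point is. If 15% and 30% are 24-month or 18-month risks, all four agree in 61% or 71%.

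**3. Does the plan call for those four tests?**

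- No sentence specifies a test at 18, 24 or 36 months.
- The sentence on categorical data is general. The Kaplan-Meier sentence is specific to freedom from relapse and stands directly before the log-rank sentence. The specific instruction governs.
- Section I joins the times with *and*. Nothing says that one significant time is enough.
- Section VI.D attaches its 5% to the log-rank test, and that test keeps it.

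The 12% therefore needs two rules that the plan does not contain.

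**4. Does the outcome variable change?**

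Criterion 6 defines *sustained* remission for entry and carries a 12-month condition. No section applies it during follow-up. Sections I, II, VI.B and IX.C all define the event as BVAS/WG of 2 or more, and section I says that such a patient has reached the primary endpoint.

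**The case for a change.** The best case for a change is that the phrase in section I is current text and speaks of deciding, while nothing calls the time points descriptive. The trial is open-label, and the investigators look at the data every six months (section IX.B). A written label on the primary analysis would protect the result from a charge of selection after the fact, and it would cost one sentence. The choice also has numerical weight, since the four results would disagree in about half of trials under 36-month risks.

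Part of this stands. The two descriptions are never reconciled, and no sentence uses the label *primary analysis*. The rest carries less weight. Most of the disagreement reflects fewer events: 24 by month 18 against 63 at close-out. A non-significant early comparison beside a significant log-rank test is expected and does not overturn it. The awkward reverse case, a time point significant when the log-rank test is not, occurs in 3% of trials. A clarifying sentence would record what VI.C and VI.D already imply, and the analysis would be the same.

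Patients withdrawn without a flare, for instance for prednisone above the limit in IX.B, raise a fair question about censoring, on which the plan is silent. It is a separate matter and does not depend on which comparison is primary.

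**Conclusion.** No change follows. The mismatch between section I and section VI.C is real, but it is a gap that analysts fill sensibly: one two-sided log-rank test of time to flare at 0.05, with the 18-, 24- and 36-month relapse-free probabilities read from the Kaplan-Meier curve. On that reading type I error is 5%, and power at 200 patients is 84% by Freedman's formula, 88% by Schoenfeld's and 86% by simulation. The 180 in VI.D stands.

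The error rate of 12% (9% with Fisher tests) is conditional on testing every time point and letting any one result decide, which the plan nowhere provides for. Guarding against it would be costly: a Bonferroni level of 0.0125 for the log-rank test needs 80 events, or 80/0.313 = 256 patients.

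The power and agreement figures assume 1:1 allocation, exponential times, no loss and, except where stated, risks that apply at 36 months, a horizon the plan does not give. The conclusion rests on the text of VI.C and VI.D and does not depend on those assumptions.

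### In this open-label trial the flare score is both the primary endpoint and the gate to relapse treatment, and nothing keeps that visit's ANCA and CD20 results from the scorer, so borderline flares could be classified differently by arm

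*Combined protocol and SAP*

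**What the plan says.** - **Masking.** Section I: "The study design is an open-label, single center, randomized and two-arm controlled trial". Neither masked scoring nor adjudication of flares appears anywhere in the document.
- **Primary endpoint.** Section VI.B: "Disease flare defined as a BVAS/WG ≥ 2".
- **Consequence of a flare.** Section I, last paragraph before the aims: such a patient "will have reached the primary endpoint and will be treated for relapse at the discretion of the investigator". Section IX.B also lists this score as a reason for withdrawal.
- **Rituximab rule, arm 1.** "Subjects will not receive rituximab if the B cell level remains < 10 cells/mm³". No provision is made for an ANCA rise.
- **Rituximab rule, arm 2.** "Rituximab will only be dosed based on the ANCA titer as described above". B-cell return plays no part.
- **Other treatment.** "Patients can be treated at any time during the study period with a total prednisone dose of ≤ 7.5 mg". Section IX.B lists a need for more than 7.5 mg daily as a withdrawal reason separate from the flare score.
- **What is measured.** Section V.E, with no distinction by arm: "The following variables will be collected at EACH study visit". The list contains the modified BVAS/WG, ANCA titer and flow cytometry. The one exception is in the arm 2 description, where CD20 testing becomes yearly once the count exceeds 90 cells/uL.
- **Who scores.** Not named for scheduled visits. Under section V.A, an investigator telephones to assess disease activity when a visit is missed.

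**The concern.** The endpoint is a clinical score with a low threshold, and crossing it changes what the clinician may do. Section I presents both ANCA rises and B-cell return as signals of coming relapse. For ANCA it reports that "100% of patients in clinical remission who sustained a fourfold rise in ANCA titer without receiving immunosuppression relapsed at mean time of 5.8 months". A scorer who sees the ignored biomarker rise therefore has a documented reason to expect relapse and, below a score of 2, no in-protocol access to rituximab. The prompt is an ANCA rise in arm 1 and B-cell return in arm 2. These need not occur equally often or carry equal weight, so any tendency to score a doubtful finding upward could differ between arms. Error of that kind shifts the treatment comparison itself and does not merely add noise.

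**Working it through.** **1. The plan's own figure.** Section VI.D gives a two-sided log-rank test at 0.05, risks of 15% and 30%, 36 months of enrollment, power 0.80 and 180 patients. Follow-up of 36 months after the last enrollment comes from section I. Assumed, because not stated: the risks apply at 36 months, relapse times are exponential, accrual is uniform and allocation is 1:1.

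- Hazard ratio: ln(0.85)/ln(0.70) = 0.456.
- Freedman events: (1.960 + 0.842)² × [(1 + 0.456)/(1 − 0.456)]² = 56.1, so 57.
- Hazard: λ = −ln(1 − p)/36. Event probability with accrual A and further follow-up F: q = 1 − [exp(−λF) − exp(−λ(F + A))]/(λA).
- With A = F = 36: q = 0.2155 and 0.4112, mean 0.313.
- N = 57/0.313 = 182, against the stated 180.

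The agreement supports these settings but does not prove them. Schoenfeld's formula with the same timing gives 163, and Freedman with a 24-month horizon and 18 months of follow-up gives 184.

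**2. Illustration of over-calling.** The documents contain no misclassification rate. I assume 3, 5 or 8 percentage points of extra flares at 36 months in one arm, with 100 patients per arm. Then d = 100(qa + qb), z = √d × (1 − HR)/(1 + HR), and the rejection probability is Φ(z − 1.96) + Φ(−z − 1.96).

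| 36-month risks | HR | d | z | Rejection |
|---|---|---|---|---|
| *No true difference* | | | | |
| 22.5% vs 22.5% | 1.000 | 63.2 | 0 | 5% |
| 22.5% vs 25.5% | 0.866 | 67.0 | 0.59 | 9% |
| 22.5% vs 27.5% | 0.793 | 69.6 | 0.97 | 16% |
| 22.5% vs 30.5% | 0.701 | 73.3 | 1.51 | 33% |
| *True 15% vs 30%, better arm over-called* | | | | |
| 15% vs 30% | 0.456 | 62.7 | 2.96 | 84% |
| 18% vs 30% | 0.556 | 66.7 | 2.33 | 64% |
| 20% vs 30% | 0.626 | 69.4 | 1.92 | 48% |
| 23% vs 30% | 0.733 | 73.4 | 1.32 | 26% |
| *True 15% vs 30%, worse arm over-called* | | | | |
| 15% vs 33% | 0.406 | 66.3 | 3.44 | 93% |
| 15% vs 35% | 0.377 | 68.7 | 3.75 | 96% |
| 15% vs 38% | 0.340 | 72.3 | 4.19 | 99% |

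**3. Sensitivity.**

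- *Accrual.* Section I gives 48 months and sections IV.B and VI.D give 36. With 48, the false-positive rates are 9%, 17% and 35%. Power goes from 87% to 68%, 51% and 28% when the better arm is over-called.
- *Both arms over-called equally.* Five points in each arm leaves the false-positive rate at 5% (27.5% vs 27.5%). At 20% vs 35%, HR = 0.518, d = 75.5 and z = 2.76, so power is 79% against 84%.
- *Scale.* On a 22.5% base, 3 to 8 points means 3/22.5 = 13% to 8/22.5 = 36% more flares. Because follow-up runs beyond 36 months, the added flares over the whole trial are somewhat more, roughly 4, 6 and 10 points.

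**The case against.** **The ANCA evidence cuts both ways.** If nearly every untreated fourfold rise leads to relapse within months, scoring such a patient upward mostly brings forward a flare that would have come anyway. With at least 36 months of follow-up, that changes the result less than a wholly extra flare, which is what the illustration models. This stands. It limits the size but does not remove the mechanism: not every doubtful score would have become a true flare, and the cited patients were without immunosuppression, so the finding may not carry over to arm 1.

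**A flare score is not the only route to treatment.** A reader might infer that it is. Prednisone up to 7.5 mg is open to both arms at any time, and needing more is a separate ground for withdrawal. The documents support only the narrower statement about rituximab and discretionary relapse treatment.

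**The scorer may not always see both biomarkers.** In arm 2, CD20 is tested yearly after it normalises. The B-cell return will already have been seen by then, so the prompt remains. That the scorer is an unmasked investigator is inferred from the open-label design and the absence of any masking text.

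**Direction is unknown.** Pressure exists in both arms and may partly cancel, and over-calling in the worse arm raises power. This stands, and it is why both branches are shown.

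**Open-label dosing is a legitimate choice.** That is so, but it does not require that the score be made with that visit's biomarker results in view.

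**Conclusion.** The concern holds as a gap in how the endpoint is protected. One score serves as both outcome and treatment trigger, the biomarker that might influence it differs by arm, and no text separates scoring from the results. Differential classification of borderline flares is therefore possible.

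A reader might go further and infer that the comparison is biased against a particular arm, or by a particular amount. The documents do not support that. They give no misclassification rate, no direction and no sign that such scoring occurs. The 9% to 33% false-positive rates, and power anywhere from 26% to 99%, follow from assumed extra flares of 3 to 8 points in one arm, the 36-month risk horizon and the stated timing. They show that a few patients per hundred would matter, not that this will happen. The sample size is unaffected. The case for acting rests mainly on how little the remedy costs.

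**What to change.** In section V.A, add that at each visit the BVAS/WG form is completed and locked from history, examination, urinalysis and creatinine before that visit's ANCA titer and CD20 count are released to the scorer. Any later change to the score should carry a date and a reason.

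The cost is the order of data entry. It needs no extra assessor, changes no sample size or treatment rule, and withholds no result from care once the form is locked.

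The limit should be stated in the plan: the arm and earlier results remain known. With visits every three months and a reported mean of 5.8 months from titer rise to relapse, a rise will often be known from a previous visit. The bias is reduced, not removed.

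Time to major relapse (BVAS-WG ≥ 3) should not be offered as the safeguard. Treatment and withdrawal at a score of 2 (sections I and IX.B) would censor it through the same scoring.
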